6.7 Toxicity Management

6.7.1 Definition - Dose Limiting Toxicity

Dose-limiting toxicities for dose-escalation purposes will be determined during the first cycle. Adverse events occurring following the first cycle will also be evaluated by

the investigator and the AbbVie Medical Monitor and may be considered as dose limiting. Any of the following events, which are considered possibly or probably related to the administration of ABT-263, will be considered a dose limiting toxicity (DLT).

- Thrombocytopenia:
 - Grade 4 thrombocytopenia ($< 25,000/\text{mm}^3$)
- Platelet counts $< 25,000/\text{mm}^3$ should be confirmed the same day by manual reading and a separate peripheral draw. If the repeat platelet count is $\geq 25,000/\text{mm}^3$, this will not be considered a DLT. If the repeat platelet count cannot be obtained within the same day as the initial measurement of $< 25,000/\text{mm}^3$, then the initial measurement will constitute a DLT.
- Grade 2 or higher bleeding associated with thrombocytopenia
- All other Grade 3, 4 or 5 adverse events will be considered a DLT. Exceptions include:
 - Grade 3, 4 Afebrile Neutropenia less than 7 days
 - Grade 3, 4 Leukopenia
 - Grade 3, 4 Lymphopenia
 - Grade 3 nausea, vomiting and/or diarrhea unless unresponsive to treatment
 - Grade 2 toxicity that requires dose modification or delay of > 1 week, will be considered a DLT (e.g., peripheral neuropathy)

Any DLT will require an interruption and possible discontinuation of ABT-263. ABT-263 may be reintroduced, but only at a reduced dose, if the toxicity grade returns to \leq Grade 1 or to baseline if Grade 2 at study entry. Following a DLT of thrombocytopenia, ABT-263 may be reintroduced, but only at a reduced dose, if the platelet toxicity grade returns to \leq Grade 2 ($\geq 50,000/\text{mm}^3$). Any reduced dose level will be jointly defined by the investigator and the AbbVie Medical Monitor. The dose may be increased thereafter upon joint determination of the investigator and the AbbVie Medical Monitor. This dose is not to exceed the highest tolerated dose level.

For the Phase 1 portion of the study, all decisions regarding continued dosing for individual subjects will be medically managed by the investigator, in conjunction with the

AbbVie Medical Monitor, as appropriate. These decisions will be driven by the definition of DLTs as described above.

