6.7.5 Determination of the MTD

The MTD is defined as the dose at which 30% of subjects experience a DLT during the first cycle. At each dose level, MTD will be estimated based on actual observations from subjects to construct a dose and toxicity rate model using the maximum likelihood method. As data accumulate and the reassessment continues, the MTD will be determined based on the convergence criteria described in Section 5.6.4. The recommended Phase 2 dose (RPTD) will be defined by observed DLTs and/or determination of MTD.

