8.1.4 Safety

Safety summaries will include all subjects participating in the study unless otherwise indicated. A safety analysis will be performed for all subjects in the Phase 1 portion of the study once the MTD is reached and/or RPTD is determined, after the last enrolled subject completes one cycle of drug, and prior to enrollment of subjects into the Phase 2a portion of the study. A second safety analysis will be performed for all subjects in the

Phase 1 and Phase 2a portions of the study upon completion of the study. The following will be included in these analyses:

Adverse Events

The number and percentage of subjects having treatment-emergent adverse events will be tabulated by MedDRA system organ class and preferred term.³⁸ The tabulations will also be provided with further breakdowns by NCI CTCAE toxicity grade and relationship to study drug. Serious adverse events, events leading to discontinuation of treatment, and events leading to death, will be summarized. For subjects who participate in Cycle 1 of Phase 1 of the study, all summaries will be done by dose. For the study as a whole, summaries will be provided with a breakdown as appropriate.

Platelet Counts

Platelet counts will be explored for trends with dose and time and summarized as appropriate. The baseline value (last measurement before the beginning of study drug administration) will be included in the statistical analysis and changes from baseline will be addressed.

A repeated measures model with dose level as a classification variable will be performed for values in Cycle 1 of the platelet counts for which multiple measurements will be taken. A transformation of a variable will be used if it clearly provides more nearly symmetric probability distribution and/or more nearly homogenous variances across dose levels.

The relationship between drug concentration variables and platelet counts will be explored. The dependence of observations from the same subject will be appropriately taken into account in all of the above analyses.

Other Safety Measurements

Laboratory test results, lymphocyte enumeration results, vital signs, echocardiogram results, and ECG interval measurements results will be explored for trends with dose and

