All analyses involving AEs were treatment-emergent adverse events (TEAE) only, unless otherwise specified. TEAE were defined as any event with onset after the first dose of navitoclax and no more than 30 days after the last dose of navitoclax. Events where the onset date was the same as the navitoclax start date were assumed to be treatment-emergent, unless the navitoclax start time and the AE start time were collected and the AE start time was prior to the navitoclax start time. If an incomplete onset date was collected for an AE, the AE was assumed to be treatment-emergent unless there was evidence that confirms that the AE was not treatment-emergent (e.g., the AE end date was prior to the date of the first dose of navitoclax).

Adverse event data was summarized and presented using primary MedDRA system organ classes (SOCs) and preferred terms (PTs) according to the MedDRA 22.0 coding dictionary.

The number and percentage of subjects experiencing treatment-emergent adverse events was summarized by phase 1 or 2, day cycle (14/21 or 21/21), navitoclax dose and for the whole portion of the study for the following adverse event summaries:

- Overview of treatment emergent adverse events
- Any treatment-emergent adverse event by System Organ Class and Preferred Term.
- Subject number associated with treatment-emergent adverse event.
- Treatment-emergent adverse events by System Organ Class, Preferred Term, and maximum NCI toxicity grade (CTCAE V3.0).

- Treatment-emergent adverse events broken down by maximum relationship to study drug.
- Any treatment-emergent NCI toxicity (CTCAE V3.0) grade 3 or 4 adverse events.
- Any treatment-emergent NCI toxicity (CTCAE V3.0) grade ≥ 3 adverse events.
- Treatment-emergent adverse events broken down by possibly or probably drug-related NCI toxicity grade ≥ 3 adverse events
- Treatment-emergent adverse events broken down by possibly or probably drug-related NCI toxicity grade 3 or 4 adverse events
- Any treatment-emergent adverse event with possibly or probably drug-related.
- For treatment-emergent serious adverse events, analyses similar to TEAE were provided.
- Any treatment-emergent adverse event leading to discontinuation of each drug.
- Any treatment-emergent adverse event leading to each drug interruption.
- Any treatment-emergent adverse event leading to each drug reduction.
- Any treatment-emergent adverse event leading to each drug delay.
- Any treatment-emergent adverse event leading to death.

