- Subject deaths occurring ≤ 30 days after last dose of study drug.
- Subject deaths occurring > 30 days after last dose of study drug.
- Any treatment-emergent DLT adverse events by primary MedDRA system organ class and preferred term.

Selected Adverse Events

Analysis of adverse events of safety areas of interest were conducted through the summary of MedDRA preferred terms identified using standard MedDRA queries (SMQs) and custom searches. Like TEAEs analyses, overview of selected AEs, and selected AEs by primary MedDRA system organ class and preferred term were provided. The search criteria for each of the safety areas of interest were described below.

Identified Risks

Thrombocytopenia - PTs: 10043554 Thrombocytopenia; 10035528 Platelet count decreased

Neutropenia - PTs: 10001507 Agranulocytosis; 10016288 Febrile neutropenia; 10029354 Neutropenia; 10059482 Neutropenic infection; 10049151 Neutropenic sepsis; 10029366 Neutrophil count decreased

Lymphopenia - PTs: 10025327 Lymphopenia; 10025256 Lymphocyte count decreased

Potential Risks

Hemorrhagic Events - SMQ 20000038 Hemorrhages (Narrow)

Opportunistic Infections - SMQ 20000235 Opportunistic Infections (Broad)

Tumor Lysis Syndrome - SMQ 20000219 Tumor Lysis Syndrome (Narrow)

Hepatotoxicity - SMQ 20000006 Drug Related Hepatic Disorders – Comprehensive (Broad); SMQ 20000007 Drug Related Hepatic Disorders – Severe Events Only (Narrow)

Increased Pancreatic Enzymes - SMQ 20000022 Acute Pancreatitis (Narrow)

Cardiovascular Events - SMQs: 20000004 Cardiac Failure (Narrow); 20000130 Pulmonary Hypertension (Narrow)

Venous Thromboembolic Events - SMQ 20000084 Embolic and Thrombotic Events, Venous (Narrow)

Cerebellar Hypoplasia - PT 10008033 Cerebellar Hypoplasia

Decreased Spermatogenesis - SMQ 20000210 Fertility Disorders (Narrow; males only)

Skin Cancer or Second Malignancies - SMQs: 20000173 Skin Neoplasms, Malignant and Unspecified (Broad); 20000090 Malignancies (Broad)

Allergic Reactions - SMQ 20000021 Anaphylactic Reaction (Broad)

Drug Interactions - HLT 10022528 Interactions

Analysis of Laboratory and Vital Signs Data

The value for baseline used in laboratory and vital sign analyses is defined in the Definition of Baseline section. All laboratory and vital signs were summarized by dose and the study portion as a whole.

Analysis of Mean Changes from Baseline in Clinical Laboratory Data

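### The SAP's Phase 1 adverse event and DLT tables by dose cover only the whole treatment-emergent window, with no first-cycle view and no stated rule for attributing dose

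*SAP*

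**What the plan says.** Protocol 8.1.4, under Adverse Events, has two consecutive sentences on breakdown: "For subjects who participate in Cycle 1 of Phase 1 of the study, all summaries will be done by dose", then "For the study as a whole, summaries will be provided with a breakdown as appropriate".

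Protocol 6.7.1 sets the DLT period: "Dose-limiting toxicities for dose-escalation purposes will be determined during the first cycle". It adds that events after the first cycle are also evaluated by "the investigator and the AbbVie Medical Monitor and may be considered as dose limiting". Protocol 6.7.5 ties the MTD to the same period: "The MTD is defined as the dose at which 30% of subjects experience a DLT during the first cycle". On the 21/21 schedule, Protocol 5.1 extends the DLT period to the lead-in plus Cycle 1.

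The SAP (Analysis of Treatment-Emergent Adverse Events) defines a treatment-emergent event as "any event with onset after the first dose of navitoclax and no more than 30 days after the last dose of navitoclax". Its grouping sentence reads: "The number and percentage of subjects experiencing treatment-emergent adverse events was summarized by phase 1 or 2, day cycle (14/21 or 21/21), navitoclax dose". The day cycle in that sentence is the dosing schedule, not a treatment cycle. The list of tables under it includes "Any treatment-emergent DLT adverse events by primary MedDRA system organ class and preferred term".

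The protocol lets dose and schedule change in Phase 1. Section 5.1 allows escalation after at least two cycles, and a switch to the recommended Phase 2a schedule once that is declared. It also keeps some 21/21 subjects on the lead-in dose. Section 6.7.1 allows reintroduction after a DLT only at a reduced dose.

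**The concern.** A table by dose shows a dose-toxicity pattern only if the events in a column arose at that dose. Over the whole treatment-emergent window this need not be so. If the SAP's dose is the assigned dose, events after escalation are counted under a lower dose than the subject was taking, and events after a reduction under a higher one. If it is the dose at onset, a subject can belong to several columns, and the SAP gives no rule for the denominators. The SAP does not say which applies.

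The DLT table has a further problem under either rule. First-cycle DLTs, which inform escalation and the MTD, share rows with later events that were judged dose limiting. A reader cannot recover the first-cycle DLT proportion at each level. At stake is how well the report describes toxicity by dose, not how the dose was chosen.

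**Working it through.** **Text side by side**

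| Item | Protocol | SAP |
|---|---|---|
| Period for Phase 1 adverse event tables by dose | Cycle 1, on the more natural reading (8.1.4) | First dose to 30 days after last dose |
| DLT period | First cycle (6.7.1, 6.7.5); lead-in plus Cycle 1 on 21/21 (5.1) | No limit beyond the treatment-emergent window |
| DLTs after the first cycle | Possible (6.7.1) | Not separated |
| Dose and schedule within a subject | Can change (5.1, 6.7.1) | No attribution rule |

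**Which reading of Protocol 8.1.4.** The Cycle 1 phrase could fix a time window or merely select subjects. Three things favour the window:
- As a selector it does almost nothing, since every treated 14/21 subject, and every 21/21 subject who finishes the lead-in, enters Cycle 1.
- The next sentence contrasts it with the whole study.
- The same section limits the repeated-measures platelet model by dose level to Cycle 1 values.

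**Timing.** Inputs from Protocol 5.1: a 21-day cycle, a 7-day lead-in (14 days if extended), and at least two cycles at a level before escalation. The plan's own 28-day DLT period is reproduced first: 7 + 21 = 28.

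| Schedule | DLT period ends | Earliest escalation |
|---|---|---|
| 14/21 | Day 21 | 2 × 21 = 42, so Day 43 |
| 21/21, 7-day lead-in | 7 + 21 = Day 28 | 7 + 42 = 49, so Day 50 |
| 21/21, 14-day lead-in | 14 + 21 = Day 35 | 14 + 42 = 56, so Day 57 |

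These days assume no interruption, because Protocol 5.1 counts the 21/21 period in days dosed. A table limited to the DLT period then holds no post-escalation events. A reduction after a DLT can still fall inside it.

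**Column sizes.** Inputs: 29 treated Phase 1 subjects (SAP, Data Sets Analyzed); four 14/21 and four 21/21 levels completed (Protocol 3.0); at least 3 subjects per cohort (Protocol 5.1).
- 4 + 4 = 8 columns; 29 / 8 = 3.6 on average.
- 29 − 8 × 3 = 5 subjects above the minimum, so at least 8 − 5 = 3 columns hold exactly 3, and none holds more than 3 + 5 = 8.
- One subject moves a column by 1/3 = 33 points at most and 1/8 = 12.5 points at least.

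This assumes that all 29 entered these levels and that each cohort met the minimum.

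**Why an all-cycle DLT proportion is a different quantity.** Illustration only: take the 30% first-cycle rate from the MTD definition, an assumed DLT probability *h* in each later cycle, and subjects followed for six cycles. The cumulative proportion is 1 − 0.70 × (1 − *h*)^5.
- *h* = 2%: 36.7%
- *h* = 5%: 45.8%
- *h* = 10%: 58.7%

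The documents give no value for *h*.

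**The case against.** The strongest reply is that the SAP does not depart from the protocol at all. Read literally, the sentence in Protocol 8.1.4 names subjects, not a period. On that reading Phase 1 tables by dose comply, and the split by schedule goes further than asked. This cannot be excluded, so a reader who infers a clear breach goes beyond the text. The DLT table and the undefined dose remain open on either reading.

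Second, Protocol 8.1.4 plans a Phase 1 safety analysis after the last enrolled subject completes one cycle and before Phase 2a enrolment. Information by dose therefore had a planned place when the dose was chosen. This lessens the harm. But the same content is required of the analysis at study completion, and the SAP's tables do not deliver the Cycle 1 view.

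Third, a reader might infer that one later DLT in a column of three, turning 0/3 into 1/3, carries that level past the 30% that defines the MTD. The documents do not support this. Protocol 8.1.1 obtains the MTD by inverting a two-parameter logistic model fitted to all the data plus down-weighted imputed and borrowed observations. A column proportion has no decision meaning, and nothing shows that any later event was classed as dose limiting.

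Fourth, a reader might extend the point to the laboratory and efficacy tables by dose. The Cycle 1 sentence stands under Adverse Events; laboratory data are to be summarized as appropriate, and the protocol's efficacy analyses concern Phase 2a. No commitment is breached there.

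Finally, the SAP lists subject numbers for each event and tabulates events leading to reduction, interruption or delay, and onset dates are collected. Events can be traced individually, but the tables do not show the first-cycle pattern.

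**Conclusion.** The point holds as a cheap reporting improvement. The SAP's adverse event and DLT tables by dose cover the whole treatment-emergent window, do not separate first-cycle from later DLTs, and leave dose undefined. Misplaced events follow only if dose means assigned dose. The failure to show the first-cycle DLT proportion holds on any reading. The Cycle 1 commitment rests on the more natural, but not the only, reading of Protocol 8.1.4.

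The tables are descriptive and the columns small, and the CRM, MTD and RPTD do not depend on them. The documents do not say how many subjects changed dose or schedule or had a later DLT, so neither the actual size nor the net direction can be given.

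**What to change.** In the SAP:

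1. Add Phase 1 adverse event and DLT tables limited to the DLT period (Cycle 1 for 14/21; lead-in plus Cycle 1 for 21/21), by initially assigned dose and schedule. Give two denominators: all treated subjects, and the evaluable subjects of Protocol 5.4.1 (a DLT, or at least 80% of first-cycle dosing). Flag events with onset during the lead-in.
2. In the all-cycle DLT table, show first-cycle and later DLTs on separate rows.
3. State for the all-cycle adverse event tables whether dose and schedule are as assigned or at onset, and how subjects who changed are counted.

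The cost is SAP wording and some reprogramming from dosing and onset dates. Each DLT-period table will hold fewer events. A reduction within the DLT period can still leave a few post-reduction events in the assigned-dose column. A first-cycle table also will not reproduce the model-based MTD; it shows the observed proportions that stand beside it.

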6.3 Relationship to Study Drug

The investigator will use the following definitions to assess the relationship of the adverse event to the use of study drug:

Probably Related An adverse event has a strong temporal relationship to study drug or recurs on re-challenge and an Other cause of event is unlikely or significantly less likely.

Possibly Related An adverse event has a strong temporal relationship to the study drug and an Other cause of event is equally or less likely compared to the potential relationship to study drug.

Probably Not Related An adverse event has little or no temporal relationship to the study drug and/or a more likely Other cause of event exists.

Not Related An adverse event is due to an underlying or concurrent illness or effect of another drug and is not related to the study drug (e.g., has no temporal relationship to study drug or has a much more likely Other cause of event).

For causality assessments, events meeting the categories of probably or possibly will be considered "associated." Events that are probably not or not related will be considered "not associated." In addition, when the investigator has not reported a causality or deemed it not assessable, AbbVie will consider the event associated.

If an investigator's opinion of possibly, probably not, or not related to study drug is given, an Other cause of event must be provided by the investigator for the serious adverse event.

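### The SAP's drug-related adverse event tables select only possibly or probably related events, whereas Protocol 6.3 also counts unreported or not-assessable causality as associated, so drug-related rates can be under-counted

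*SAP*

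**What the plan says.** Protocol section 6.3 (Relationship to Study Drug) gives the investigator four categories: probably, possibly, probably not and not related. It then groups them: "events meeting the categories of probably or possibly will be considered" associated, and the two lower categories are not associated. A further sentence sets a default: "when the investigator has not reported a causality or deemed it not assessable, AbbVie will consider the event associated". Protocol section 8.1.4 promises adverse event tables by relationship without naming the categories: "The tabulations will also be provided with further breakdowns by NCI CTCAE toxicity grade and relationship to study drug".

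The SAP, under Analysis of Treatment-Emergent Adverse Events, lists the tables. Those restricted to drug-related events are described as "Any treatment-emergent adverse event with possibly or probably drug-related" and "Treatment-emergent adverse events broken down by possibly or probably drug-related NCI toxicity grade ≥ 3 adverse events", with a grade 3 or 4 version of the latter. Serious events are to be analysed in a similar way. A separate table is described as "Treatment-emergent adverse events broken down by maximum relationship to study drug", with no categories or ranking given. The SAP does not mention missing or not-assessable causality.

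**The concern.** The protocol has three routes to an associated event and the SAP tables name two. If the tables were programmed from the SAP text alone, an event with a blank or not-assessable causality would appear in no drug-related table, although the sponsor's own rule classes it as associated. Any such omission lowers the drug-related count.

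Safety assessment is the first-listed objective of all three portions of the study, and these tables are where drug-related toxicity is reported. The denominators are small, so even one subject is visible in a percentage.

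**Working it through.** The documents give no drug-related event count and no count of events with missing causality, so there is no plan figure to reproduce. The check compares the two texts and then sets a scale.

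**Step 1: compare the selections.**

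| Causality recorded | Protocol 6.3 | SAP drug-related tables |
|---|---|---|
| Probably related | associated | selected |
| Possibly related | associated | selected |
| Not reported or not assessable | associated | not named |
| Probably not related, not related | not associated | not selected |

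Read literally, the SAP selection is a strict subset of the protocol's. A count on the SAP selection is therefore at most equal to a count on the protocol's, so any error is towards too few.

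**Step 2: look for the third route elsewhere in the SAP.** The SAP does state rules for incomplete adverse event data where it wants them. For dates: "If an incomplete onset date was collected for an AE, the AE was assumed to be treatment-emergent unless there was evidence" to the contrary. An incomplete medication start date is likewise resolved towards concomitant use. Both defaults are inclusive. There is no counterpart for causality.

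**Step 3: consider the maximum-relationship table.** A maximum needs an ordering. Neither document ranks a missing or not-assessable value against the four categories, so the table is undefined for such events.

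**Step 4: scale.** Let k be the number of subjects who enter a given drug-related table row only through an event with missing or not-assessable causality. The change in a by-phase percentage is 100 × k/N. The SAP (Data Sets Analyzed) gives N = 29 for Phase 1 and N = 31 for Phase 2. The values of k are assumed, for scale only.

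| k (assumed) | Phase 1, k/29 | Phase 2, k/31 |
|---|---|---|
| 0 | 0 | 0 |
| 1 | 3.4 points | 3.2 points |
| 2 | 6.9 points | 6.5 points |
| 3 | 10.3 points | 9.7 points |

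Within a dose level of n subjects, one subject is worth 100/n points. This exceeds the by-phase figure whenever n is below the phase total.

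**Step 5: what a non-zero k requires.** At least one treatment-emergent event must lack a usable causality. That event must not have been recoded as related before tabulation. The subject must have no other possibly or probably related event in the same row. The documents establish none of these.

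**The case against.** The strongest reply is that the gap may have no effect. Protocol 6.0 requires the investigator to assess and record the relationship for any adverse event. The four categories in section 6.3 offer no not-assessable option. Sections 10.2, 10.3 and 11.0 add investigator review of the forms for completeness, full source document review and continuous sponsor review. The default in 6.3 looks like a fallback, and it describes how the sponsor classifies an event, not how a table is built. If it was applied before tabulation, the events are already in the tables. The protocol itself uses a possibly-or-probably criterion for dose-limiting toxicity in section 6.7.1. Finally, the all-causality tables, including those by grade, seriousness, discontinuation and death, do not depend on the causality field, so no event disappears from safety reporting.

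Most of this stands as a limit on size. It does not remove the mismatch. The default in 6.3 is not confined to serious events or to expedited reporting, and 6.3 is where the protocol defines the relationship that 8.1.4 says will be tabulated. The dose-limiting toxicity criterion serves dose escalation and does not define drug-related for the safety tables. Whether events were recoded beforehand cannot be learned from the SAP.

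Two stronger readings should be resisted. A reader might infer that an unassessed event leaves its subject shown as not related in the maximum-relationship table; the SAP specifies no such behaviour. A reader might also quote a 33-point shift from one subject in three. Three is only the protocol's minimum cohort size, and the actual dose-level sizes are not given.

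**Conclusion.** The point holds as a conflict of definitions: the SAP states a selection narrower than the protocol's rule, and following it literally can only under-count drug-related events. The size is 3.4 points per affected subject in Phase 1 and 3.2 points in Phase 2, more within a dose level, multiplied by an unknown number of subjects that may be zero.

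A reader might infer that drug-related toxicity was in fact under-reported. The documents do not support that, because they show neither that such events occurred nor that they were left unmapped. Nor do they support any percentage range for the shortfall, since any assumed share of affected subjects would simply be returned as the result. No dose decision or efficacy result is shown to depend on these tables. The change is still worth making, because a reader of the current text cannot tell which rule was applied.

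**What to change.** Add one sentence to the SAP defining a drug-related event, with reference to Protocol 6.3, as one whose causality is possibly related, probably related, not reported or not assessable. Apply it to every drug-related table: any grade, grade 3 or 4, grade 3 and above, and the serious-event versions. Count such events as related in the maximum-relationship table too, and state the rank they take, because 6.3 calls them associated without choosing between possible and probable. Footnote each table with the number of events so handled, including when it is zero.

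The cost is one sentence and one programming line. The SAP is written in the past tense, so the count can be checked against existing data. If it is zero, the footnote closes the question. If not, the affected tables need rerunning and the drug-related percentages may rise slightly.
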